For this study, we will be implementing the full version of the online support group intervention piloted in the feasibility study and conduct a randomized controlled trial to evaluate its impact on retention in HIV care services. The intervention components include:

- Informational messages that reflect the content of the structured group counseling curriculum, • Positive Connections, and are posted to the group wall on a regular basis several times a week, for approximately 4 to 4.5 months
- Moderated, closed group chats in a "secret" Facebook group where YLHIV can interact with their peers and with a trained health counselor
- Access to a trained counselor via Facebook Messenger or phone for the duration of the intervention who will be able to provide information or basic counseling on ART/HIV care related issues, with referral to health care services as needed

Ι. Study Aim and Objectives

The principle aim of this research is to gather evidence on an intervention designed to improve retention in HIV care services among youth living with HIV, ages 15-24 years, enrolled in ART services.

The objectives of the study are:

- 1. To test the effectiveness of a structured online support group (SMART Connections) to increase retention in HIV services among YLHIV.
- 2. To examine the effect of the SMART Connections on secondary outcomes of social support, HIV knowledge and treatment literacy, and ART adherence among YLHIV.
- 3. To test the potential mediating effect of social support on the relationship between the intervention and primary outcome.
- 4. To document the costs of the intervention and calculate the unit cost per YLHIV retained. Intervention costs will also be descriptively compared to the costs of adolescent-focused, in-person support groups in the region.
- 5. To document participant engagement and perspectives regarding the content and delivery of the intervention to inform scalability and sustainability.
- 6. To document implementation and health care provider and support group facilitator perspectives regarding intervention content and delivery to inform scalability and sustainability.

The study's primary outcome is retention in HIV services at 6-9 months after enrollment. The study's secondary outcomes are:

- 1. ART adherence
- 2. Social support

3. HIV knowledge and treatment literacy

11. Study Design

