For the survival analysis, we will create two sets of variables indicating retention using a 28 day cutoff and using a 90 day cutoff to reflect the fact that the national guidelines for retention in HIV services changed from 12 weeks (i.e. 90 days) to 4 weeks (i.e. 28 days). For each recorded visit, we will also assess whether the participant is within their scheduled window and the number of days between the scheduled visit date and the date the visit was actually attended (v1 denotes the first attended visit after study enrollment; v2, v3, v4, etc. will be calculated for all visits between study enrollment and date of EL questionnaire (or date EL questionnaire should have been conducted, based on enrollment date, for those LTFU in the study at endline):

For each visit, starting at visit 2 (i.e. v2):

- v2_days_aftersched = [visit date (v2q036)] [date of prior scheduled visit (v1q044)]; missing if either date is . or jan 1 1990
- v2_ltfu_28 = 1 if v1_days_aftersched >28; = 0 if v1_days_aftersched ≤28; missing if next scheduled visit date (v1q044) is missing (. or jan 1 1990).
- v2_ltfu_90 = 1 if v1_days_aftersched >90; = 0 if v1_days_aftersched ≤90; missing if next scheduled visit date is missing (. Or jan 1 1990).

1tfu 28 LTFU status for survival analysis using 28 day cutoff

- **ltfu_28**=1; lost to follow-up
 - o v2 ltfu 28==1 OR v3 ltfu 28==1 OR v4 ltfu 28==1, etc.
 - o Appears retained for all recorded visits, but earliest value of today_el, today_el_approx, latest_mre falls MORE than 28 days after latest instance of vnq044
- ltfu 28=0; retained

- o v2 ltfu 28==0 AND v3 ltfu 28==0 AND v4 ltfu 28==0, etc. AND the earliest value of today el, today el approx, latest mre falls within 28 days of latest instance of **vnq044**
- 1tfu 28=8; transferred out
 - o Retained up to the date of transfer (transfer==1 and q027, transfer date, must be non-missing)
- **ltfu 28**=9; died
 - o Retained up to the date of death (death==1 and q028, death date, must be non-missing)

1tfu 90 LTFU status for survival analysis using 90 day cutoff

- **ltfu 90**=1; lost to follow-up
 - o v2 ltfu 90==1 OR v3 ltfu 90==1 OR v4 ltfu 90==1, etc.
 - o Appears retained for all recorded visits, but earliest value of today el, today el approx, latest mre falls MORE than 90 days after latest instance of **vnq044**

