 - q027>today_bl AND latest follow-up date prior to transfer is missing
 t ltfu 90=9
- if **ltfu_90=9**
 - o ret_time_90=q028-today_b1

Missingness will be handled in the following way:

- If a follow-up date (i.e. **v7q044**) is missing (. or Jan 1 1990) and retained up to that point, retention must be assessed using the clinic visit date at which the follow-up date is missing. Consider retention time to be the visit date + 28 days as a conservative estimate of the follow-up time. Consider censored if retained up to that point.
- If a participant has died [died==1] but is missing date of death [q028] and appears to be retained throughout the entire study period, retention time is assessed based on the latest attended visit (i.e. v2q036), given that we do not know if participant died prior to the scheduled follow-up date.
- If a participant has transferred [transfer==1] but is missing date of transfer [q027] and appears to be retained throughout the entire study period, participant is categorized as transferred (ltfu_28/ltfu_60/ltfu_90==8) and retention time is assessed based on the latest available follow-up date (i.e. v7q044)
- If medical record data are incomplete towards the end of the study period (i.e. **latest_mre** falls before **today_el/today_el_approx**), then retention is assessed using **latest_mre** as the pseudo-endline date. Retention cannot be assessed into the future.
- If no visit data for participant during the study period or all visit dates for participant are missing during the study period (. or jan 1 1990), then retention time is missing and LTFU status is missing.
- We will generate a variable, conservative, to indicate whether participants have complete medical record data (conservative=1) or have a gap during the beginning of the study period conservative=.).

conservative=1 if (v1q036-today_bl)<=56 & v1q036!=.

conservative=. otherwise

Other variables for descriptive analysis of retention data

Other variables will be created to describe retention and clinic visits during the study period:

n_visits=number of clinic visits attended during the study period

• Code:gen n_visits=.

```
forvalues i=11(-1)1 {
replace n_visits=`i' if v`i'q036!=. & n_visits==. & ((v`i'q036<=today_el &
today_el!=.) | (v`i'q036<today_el_approx & today_el_approx!=.))
}
replace n visits=0 if v1q036==. | ( v1q036<today bl & v2q036==.)</pre>
```

n missed 28=Number of clinic visits missed by more than 28 days during the study period

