Two main assumptions underlie the multiple imputation procedure. First, the data are assumed to be missing at random (MAR). According the SAS User Guide (2003a), for a variable to be MAR, "the probability that an observation is missing can depend on the observed variable values of the individual, but not on the missing variable values of the individual." Although the MAR assumption cannot be verified, since independence from the missing values cannot be estimated, Schafer states that the assumption becomes more plausible as the number of variables included in the imputation model increases (Schafer, 1997). We will assess MAR and verify that there is no reason to think the missing-at-random assumption is violated using the mi misstable patterns command specified for the variables to be included in the multiple imputation. The second assumption is that of multivariate normality. However, according to Schafer (1997), inferences based on multiple imputation can be robust to departures from the assumption if the amount of missing data is not large.

The mi set of commands (mi set, mi impute, and mi estimate) will be used for the multiple imputation procedure. To allow results to be reproducible, a random-number seed will be set. M=10 imputed datasets will be created.

For participants that have complete medical record for the study period (i.e. conservative=1, ltfu 28!=. and ret time 28!=0), we will also descriptively present the following by ITT intervention arm:

- n visits=number of clinic visits attended during the study period
- n missed 28=Number of clinic visits missed by more than 28 days during the study period •
- mean followup mo=Mean months of follow-up time during the study period ٠

Objective 2.

To examine the association between treatment exposure and secondary outcomes of social support, HIV knowledge and treatment literacy, adherence and viral suppression, we will conduct significance testing using two-sided tests, with an alpha of 0.05. To examine the relationship between treatment exposure and social support, a continuous variable, we will conduct a t-test using treatment exposure (group) and change from baseline to endline in social support score (ss avg chng). We will similarly examine the relationship between treatment exposure and HIV knowledge by conducting a t-test using treatment exposure (group) and change from baseline to endline in total knowledge score (know chng).

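### The by-arm clinic-visit counts have no observation-time denominator, and their code screens neither the 1 Jan 1990 missing-date code nor records that end early

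*SAP*

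**What the plan says.** **The table.** SAP section VI, Objective 1, lists three descriptive items by randomised arm: "n visits=number of clinic visits attended during the study period", `n_missed_28` (visits missed by more than 28 days) and `mean_followup_mo`. The population is described as having a complete record over the study. In code this means `conservative=1`, `ltfu_28` not missing and `ret_time_28` not zero.

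**The completeness flag.** Section IV.C says that participants who fail the flag "have a gap during the beginning of the study period". The code is "conservative=1 if (v1q036-today_bl)<=56 & v1q036", followed by a test that the first visit date is not Stata-missing.

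**The count.** The loop in section IV.C runs from visit 11 down to visit 1 and takes the first index that qualifies: "replace n_visits=`i' if v`i'q036!=. & n_visits==. & ((v`i'q036<=today_el", with a parallel clause for the approximate endline. One later line resets the count: "replace n visits=0 if v1q036==. | ( v1q036<today bl & v2q036" is also Stata-missing.

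**Missing dates.** The missingness rules in section IV.C give 1 Jan 1990 the same status as Stata-missing. A participant for whom "all visit dates for participant are missing during the study period (. or jan 1 1990") has LTFU status missing. The lateness variable that feeds `n_missed_28` is set to "missing if either date is . or jan 1 1990".

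**The window.** Section I states: "The study's primary outcome is retention in HIV services at 6-9 months after enrollment". Section IV.C sets endline at each participant's own interview date, or at an approximation based on others enrolled in the same month. It also foresees records that stop before endline (`latest_mre` earlier than endline) and moves the end date for retention, but not for the visit counts.

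**The concern.** A reader of the table will take a difference in visit counts between arms as a difference in attendance. The count also depends on how long each record was observed, because endline varies and some records stop early, and nothing in the table shows that time. The completeness label suggests that early-ending records were removed, but none of the three conditions tests the end of the record.

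The code adds a second problem. The SAP uses two codes for an unknown date, and the lines for `conservative` and `n_visits` reject only one of them. A 1 Jan 1990 entry is numerically a very early date, so it satisfies any condition of the form on or before a given date.

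What is at stake is the SAP's by-arm count of visits attended and missed. The protocol (Analyses, Primary Objective) also promises a descriptive account of lapses in care.

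**Working it through.** The documents give no figure for these counts, so there is none to reproduce. The check applies the SAP code, line by line, to constructed visit histories.

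**Inputs**
- Rules for `conservative` and `n_visits`: SAP section IV.C.
- Visit spacing: 30 days (assumption; the protocol's footnote to Figure 1 describes typical monthly refills).
- Baseline: 1 October 2018 (assumption; any baseline in 2018 gives the same result).
- Endline: day 180 or day 270, the ends of the 6-9 month range in SAP section I.

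**1. Unequal windows.** Rate = visits ÷ (days observed ÷ 30.44).

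| Perfect monthly attender | Days observed | `conservative` | `n_visits` | Visits per month |
|---|---|---|---|---|
| Endline day 270 | 270 | 1 | 9 | 9 ÷ 8.87 = 1.01 |
| Endline day 180 | 180 | 1 | 6 | 6 ÷ 5.91 = 1.01 |
| Record ends day 120, endline day 270 | 120 | 1 | 4 | 4 ÷ 3.94 = 1.01 |

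Attendance is identical, the counts are 9, 6 and 4, and all three pass as complete. Between the two ends of the endline range the ratio is 9 ÷ 6 = 1.5. This compares two individuals; it is not an arm difference.

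**2. Placeholder and the start-gap flag.** 1 Jan 1990 minus 1 October 2018 = -10,500 days. This is at most 56, and the date is not Stata-missing, so the flag is 1.
- First visit undated (1 Jan 1990), then real visits at days 150, 180, 210, 240 and 270: `conservative=1`, `n_visits=6`, with 5 dated visits in the window.
- The same history without the placeholder: 150 is above 56, so `conservative` is missing and the participant leaves the table.

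The placeholder therefore admits the early gap that the flag is meant to catch.

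**3. Placeholder after endline.** Six real visits to day 180, two visits at days 280 and 310 (after endline at day 270), then an undated ninth visit: `n_visits=9`, with 6 in the window. One undated entry adds three because the loop returns the visit's index number.

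**4. First visit before baseline.**
- First visit at day -20, second at day 200: the reset line does not apply because a second visit exists. Result: `conservative=1`, `n_visits=2`, with 1 in the window.
- First visit at day -20 and no second visit: `n_visits=0`, so the reset works here.

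**5. Where existing guards work.**
- All visit dates are placeholders: the code alone gives `conservative=1` and a positive count, but `ltfu_28` is missing and the participant is excluded.
- `n_missed_28`: its lateness input excludes the placeholder, so no placeholder defect is shown. It shares only the missing denominator and the population filter.
- `mean_followup_mo`: it divides by `n_visits` (section IV.C), so an error in that count enters its denominator.

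**The case against.** The strongest reply is that the table is descriptive, has no test attached, and mostly works on clean data. Several parts of it stand.

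- With clean dates and equal windows, `n_visits` is attendance. A reader might infer that the counts measure record coverage instead of attendance. The documents support only that they mix the two.
- A reader might infer that both counts are corrupted by the placeholder. Section IV.C screens it from the input to `n_missed_28`, and records with no usable visit date are excluded altogether. The defect is confined to partly dated records.
- Section IV.C numbers visits from the first one attended once the participant is enrolled, so a pre-baseline first visit should not occur. The reset line shows that the authors allowed for one, but the documents do not show that any exists.
- An undated entry between two dated in-study visits is plausibly a real visit. Counting it is defensible, and dropping it would undercount attendance.
- A reader might infer bias between arms. Allocation is randomised 1:1, and nothing in the documents shows interview timing, extraction or undated visits differing by arm.
- By-arm retention is also shown by Kaplan-Meier curves and proportions retained, so this is not the only view of attendance.
- Visits per month depend on the scheduled interval: a perfect attender on longer refills scores lower. A rate alone is not a full answer either.

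The reply does not explain why a population labelled complete is untested at the end of the record, or why two derivations omit a missing code that neighbouring rules respect.

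**Conclusion.** The point holds as a minor one, limited to the descriptive by-arm table. `n_visits` and `n_missed_28` are raw totals over participant-specific windows, and the completeness filter checks only the start of the record. As coded, a 1 Jan 1990 date at the first visit defeats that filter, and one placed after endline is counted as in-study. A pre-baseline first visit, if any occurs, passes the filter and is counted whenever a second visit exists.

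The sizes rest on assumed 30-day visits and constructed histories: counts of 9, 6 and 4 at one and the same attendance rate, and one to three surplus visits in the placeholder and pre-baseline examples above. The effect in the real data cannot be computed, because the documents do not give the number of such dates. Any arm imbalance is likewise unknown. The log-rank test uses neither `n_visits` nor `conservative`, so the documents do not support extending the concern to the primary analysis.

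**What to change.** In SAP section IV.C and the code:

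1. Recode 1 Jan 1990 to Stata-missing before any of these variables is derived.
2. Compute `conservative` from the first dated visit on or after `today_bl`.
3. Count visits dated from `today_bl` to the earliest of endline, `latest_mre`, transfer and death. Keep an undated visit only when it lies between two dated visits inside that window.
4. In section VI, report observed time by arm, with visits and misses of more than 28 days per observed month beside the raw counts. Read these together with the scheduled follow-up interval.

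Observed time must stop at transfer and death; otherwise participants accrue months in which no study-clinic visit was possible.

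Cost: SAP wording and a little extra code, on dates already planned for abstraction. Some records with an early gap that now pass will leave the table.

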Code: egen n_missed_28=rowtotal(v2ltfu_28 v3ltfu_28 v4ltfu_28 v5ltfu_28 v6ltfu_28 v7ltfu_28 v8ltfu_28 v9ltfu_28 v10ltfu_28 v11ltfu_28)

mean_followup_mo=Mean months of follow-up time during the study period

• Code: forvalues i=1/11{

```
gen v`i'fu=v`i'followup if ((v`i'q036<=today_el & today_el!=.) |
(v`i'q036<=today_el_approx & today_el_approx!=.))
}
egen followup_total=rowtotal(v1fu v2fu v3fu v4fu v5fu v6fu v7fu v8fu v9fu
v10fu v11fu)
gen mean_followup=followup_total/n_visits
gen mean_followup_mo=floor(mean_followup/30.44)
replace mean_followup_mo=1 if mean_followup_mo==0</pre>
```

Timeliness of scheduled intervention activities

Timeliness of each scheduled intervention activity, including scheduled postings and group chats, will be calculated using Facebook group data from Grytics to evaluate the extent to which each group was implemented as planned. The difference between the scheduled date and the actual date will be calculated for each intervention activity; timeliness will be dichotomized with activities coded as timely if they occurred within one week of the scheduled time, and untimely if they occurred outside of this one-week window. The proportion of missing data will be reported.

High and low intervention engagement

Facilitators will be asked to identify the highest- and lowest-engaged participants in their Facebook groups. High and low engagement participants will be recruited at endline to participate in IDIs.

Social Support [MOS-SSS]¹

People sometimes look to others for companionship, assistance, or other types of support. How often is each of the following kinds of support available to you if you need it?

Factor	Item	Item
	no.	
Emotional/	1	Someone you can count on to listen to you when you need to talk
support	2	Someone to give you information to help you understand a situation
	3	Someone to give you good advice about a crisis
	4	Someone to confide in or talk to about yourself or your problems
	5	Someone whose advice you really want

	6	Someone to share your most private worries and fears with
	7	Someone to turn to for suggestions about how to deal with a personal problem
	8	Someone who understands your problems
Tangible support	9	Someone to help you if you were confined to bed
	10	Someone to take you to the doctor if you needed it
	11	Someone to prepare you meals if you were unable to do it yourself
	12	Someone to help with daily chores if you were sick
Affectionate support	13	Someone who shows you love and affection

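### As coded, the SAP's count of visits missed by more than 28 days adds nothing for a final non-return, so the by-arm table does not show what its label says

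*SAP*

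**What the plan says.** SAP section IV.C, under the other variables for descriptive analysis of retention data, labels the variable "n missed 28=Number of clinic visits missed by more than 28 days during the study period". Its code is "egen n_missed_28=rowtotal(v2ltfu_28 v3ltfu_28 v4ltfu_28" and the corresponding flags up to visit 11, with no other term.

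The flags are built under the retention variables for survival analysis in the same section:

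- Visits are indexed by attendance: "v1 denotes the first attended visit after study enrollment".
- Lateness is the attended date minus the previously scheduled date, and is "missing if either date is . or jan 1 1990".
- The flag is defined as "v2_ltfu_28 = 1 if v1_days_aftersched >28; = 0 if v1_days_aftersched ≤28; missing if next scheduled visit date (v1q044) is missing". No value is given for a participant who has a scheduled date but never attends.
- `ltfu_28`, the survival status, has a second route to loss: "Appears retained for all recorded visits, but earliest value of today_el, today_el_approx, latest_mre falls MORE than 28 days after latest instance of vnq044".

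SAP section VI, Objective 1, presents the count descriptively by intention-to-treat arm, beside `n_visits` and mean follow-up months. The table is limited to participants with `conservative=1` (first visit within 56 days of baseline), a non-missing `ltfu_28` and a non-zero `ret_time_28`.

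**The concern.** A participant who is on time at every recorded visit and then disappears has no further attended date, so no lateness value and no flag. Stata's `rowtotal` counts a missing flag as zero. The final non-return, the most serious kind of missed visit, contributes nothing.

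The second route into `ltfu_28` is needed because the per-visit flags cannot detect this case. It was not carried into `n_missed_28`. The same person is then lost in the survival analysis and has no missed visits in the supporting table. The conditions that limit the table do not remove such a person, provided that the first visit fell within 56 days.

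What is at stake is a descriptive comparison of arms whose figures can point the wrong way.

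**Working it through.** The SAP gives no expected value for this count, so there is no plan figure to reproduce. The check has two parts.

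**1. Tracing the code on worked histories** (monthly visits, endline at day 270)

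| History | `n_missed_28` as coded | Lost under `ltfu_28`? | With final non-return added |
|---|---|---|---|
| On time throughout | 0 | No | 0 |
| On time at v1 to v3, never returns | 0 | Yes, second route only | 1 |
| v1 only, never returns | 0 | Yes, second route only | 1 |
| One return 35 days late, then stays | 1 | Yes, by flag | 1 |
| One late return, later never returns | 1 | Yes, both routes | 2 |

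The second and third histories leave about 5 and 7 monthly visits unattended, yet match the first.

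**2. Expected count per arm**

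Inputs from the documents: 12-month retention S of 0.45 (control) and 0.575 (intervention), with exponential times (SAP section III, Sample size), and typically monthly visits (Protocol, Background, footnote to Figure 1).

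Assumptions: all loss is permanent, and q, the probability that a visit is reached by a return more than 28 days late, is the same in both arms. I use q = 0.02, 0.05 and 0.10.

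Nine monthly visits over 270 days give eight flags, so the coded expectation is q × Σ S^((k−1)/12) for k = 2 to 9.

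- Control sum: 5.999. Intervention sum: 6.537.
- At q = 0.05: 0.05 × 5.999 = 0.300 and 0.05 × 6.537 = 0.327.

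Permanent loss by the ninth visit is 1 − S^(8/12):

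- Control: 1 − 0.45^(8/12) = 0.413. Intervention: 1 − 0.575^(8/12) = 0.309.

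Counting the final non-return adds these amounts.

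| q | As coded: control vs intervention | Final non-return counted: control vs intervention |
|---|---|---|
| 0.02 | 0.120 vs 0.131 | 0.533 vs 0.439 |
| 0.05 | 0.300 vs 0.327 | 0.713 vs 0.635 |
| 0.10 | 0.600 vs 0.654 | 1.013 vs 0.962 |

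As coded, control has the lower count at every q, because fewer of its participants remain to return late. The ordering holds until control's late-return rate is about 9% higher in relative terms (6.537 / 5.999 = 1.09). Over all 11 visits the margin is about 11% (7.828 / 7.063 = 1.11).

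The corrected order also has a limit. The addition favours intervention by 0.413 − 0.309 = 0.104, and the coded part works against it by q × (6.537 − 5.999) = 0.538q. Control stays higher only while q is below about 0.104 / 0.538 = 0.19. The count therefore needs to be read beside `n_visits`.

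**The case against.** **The table is descriptive.** It has no test and feeds no other analysis, and `n_visits` next to it would show an early dropout's few visits. This stands and limits the weight of the point. It does not make the label true.

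**The count has a legitimate use.** The Protocol's analysis section plans to describe lapses in care and return to treatment, and a tally of lapses that ended in a return fits that purpose. This is a fair reading of intent, but the SAP's label says "Number of clinic visits missed by more than 28 days during the study period", which a final non-return plainly is.

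**The flag is under-specified.** It is set to missing only when the scheduled date is missing. If Stata's treatment of missing values as large were allowed to apply, a never-returner would score 1. So would a fully retained participant whose next visit is not yet recorded, who would then be classed as lost, against the SAP's own definition of retained. That reading does not rescue the count.

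**Three stronger readings are tempting, and the documents do not support them.**

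- *The table could contradict the primary result, because an intervention that turns permanent loss into late return would show more missed visits.* Any single return more than 28 days late already sets `ltfu_28` to 1. That conversion does not improve the primary outcome, so there is no favourable result for it to contradict. At most there could be tension with the secondary 90-day analysis, for returns 29 to 90 days late.
- *Planned loss by day 270, about 0.45 and 0.34, is a lower bound on the understatement.* Those figures come from 1 − 0.45^(270/365.25) and 1 − 0.575^(270/365.25). The planned rates belong with the Protocol's three-month definition of loss, would be applied here to everyone randomised and not to the restricted table, and do not say how many of those lost never return.
- *Everyone who stops attending scores zero.* Someone with a previous late return keeps that count, although the final loss still adds nothing. Someone with no visit after baseline is left out of the table.

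**Conclusion.** The point holds as a coding error in a descriptive table. `n_missed_28` counts only scheduled visits followed by a return more than 28 days late, so a participant who attends on time and then leaves for good is indistinguishable on it from a perfect attender.

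The coded difference between arms is small, 0.011 to 0.054 visits per participant over the q values tried, but its direction is wrong for the label, and it reverses once the final non-return is counted. These sizes are illustrations. They rest on the planned retention rates, permanent loss, monthly visits and equal late-return rates in the two arms; only the first and the visit spacing come from the documents. That a final non-return scores zero rests on the natural reading of the flag and on how `rowtotal` handles missing values, not on those rates.

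The primary log-rank comparison uses `ltfu_28` with its second route and is not affected.

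**What to change.** Add 1 to `n_missed_28` when `ltfu_28` is 1 and the earliest of `today_el`, `today_el_approx` and `latest_mre` is more than 28 days after the last scheduled date (`vnq044`), with no later attended visit. Leave out transfers (code 8) and deaths (code 9). A participant with a previous lapse who later transfers or dies can still carry code 1, so the transfer and death dates should be checked too.

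Describe the variable as the number of lapses of more than 28 days, including a final non-return, and show it beside `n_visits`. It is then a count of lapses, not of every unattended appointment. A denominator of visits due is not available, because the SAP records scheduled dates only with attended visits and later ones would have to be imputed.

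The SAP should also say what the per-visit flag is when a visit was scheduled and no attended date exists.

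The cost is one or two lines of code using variables already defined and a sentence or two in the SAP.
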